### 4.2 Treatment Groups

The single treatment group is zavegeptan 10 mg.

### 4.3 Subgroups

The following safety subgroups are of interest for the safety analysis set:

- Intrinsic factors
  - Age at informed consent (years):  $< 40$ ,  $\geq 40$ ,  $< 65$ ,  $\geq 65$
  - Sex: female, male
  - Race: White, Black or African American, other including Asian, Asian
  - Ethnicity: Hispanic or Latino, not Hispanic or Latino
  - Cardiovascular risk factors contraindicating triptans: yes, no (refer to the Zavegeptan Core SAP)
  - Baseline body mass index (BMI;  $\text{kg}/\text{m}^2$ ):  $< 25$ ,  $\geq 25$  to  $< 30$ ,  $\geq 30$

- Extrinsic factors
  - Average zavegepant exposure (sprays per month): < 6,  $\geq$  6 (see Section 6.2.5.1).
  - Cumulative zavegepant exposure (sprays): < 20,  $\geq$  20 to < 40,  $\geq$  40 to < 60,  $\geq$  60 to < 80,  $\geq$  80 (see Section 6.2.5.1)
  - Time on zavegepant (weeks): < 12,  $\geq$  12 to < 24,  $\geq$  24 to < 36,  $\geq$  36 to 48,  $\geq$  48 (see Section 6.2.5.1)
  - Concomitant prophylactic migraine medication use: yes, no (see Section 6.2.5.4)
  - Current or concomitant approved biologics use (yes, no; see Section 6.2.5.4)
  - Total treated migraine days per month in the overall LTT (< 2,  $\geq$  2; see Section 6.4.6.2).

Subgroup tables present results by subgroup level and overall for subjects with non-missing subgroup level data. Subgroup levels may be redefined or combined based on the availability of data.

## 5 SAMPLE SIZE, POWER, AND TYPE 1 ERROR

With a sample size of 600 treated subjects and no events observed, the upper bound of a one-sided 95% confidence interval for zero observations is 0.005. Hence this sample size is large enough to rule out AEs that occur at rates greater than 5 cases per 1,000 subjects.

## 6 STATISTICAL ANALYSES

All statistical analyses are performed using SAS statistical software (Version 9.4 or higher).

### 6.1 General

#### 6.1.1 *Programmed Output*

A list of TLFs and corresponding templates are presented separately in a mock TLF document corresponding to this SAP.

Tables present results by the single treatment group (i.e., zavegepant 10 mg).

Refer to the Zavegepant Core SAP for additional details about programmed output.

##### 6.1.1.1 *Time-to-event Tables and Plots*

Time-to-event endpoints are summarized with Kaplan-Meier tables and plots. Refer to the Zavegepant Core SAP for additional details.

##### 6.1.1.2 *Listings*

Unless specified otherwise, by-subject listings are sorted by treatment status (treated, not treated), site-subject ID, and additional variables such as time points, as applicable.

All listings except listings of batch numbers identify subjects who are impacted by COVID-19 (see Section 9.1.2).

Listings of significant protocol deviations, non-study medications, safety parameters, outcomes research parameters, and COVID-19 visit impact display both study day and treatment day (see Section 7.3). Other listings display study day only, if applicable.

Listings of significant protocol deviations, safety parameters, outcomes research parameters, and COVID-19 visit impact include the following: abbreviated name of the analysis period in which the measurement was slotted (i.e., PRELLT, LTT, FU; this does not apply to outcomes research parameters); analysis visit in which the measurement was slotted (this does not apply to AEs); measurement date/time; study day and treatment day derived using the measurement date.

Select listings of measurements over time display COVID-19 visit impact code for visits that are impacted by COVID-19 (see Section 9.1.5.2).

Refer to the Zavegeptan Core SAP for additional details about listings.

### **6.1.2 *Statistical Methods***

Refer to the Zavegeptan Core SAP for descriptive statistics in summary tables, counting rules in frequency tables, and rounding rules.

### **6.1.3 *Missing Data***

All analyses are based on observed data without using imputation.

## **6.2 *Study Population***

### **6.2.1 *Analysis Sets***

The number of subjects in each analysis set described in Section 4.1 is tabulated.

A by-subject listing of analysis sets is provided for the enrolled analysis set. Refer to the Zavegeptan Core SAP for listing contents.

### **6.2.2 *Enrollment***

Enrollment by (1) country and site and (2) age group are tabulated for the enrolled analysis set. The enrollment by country and site table also displays results for the full and safety analysis sets. Refer to the Zavegeptan Core SAP for additional details.

Accrual by month and year of LTT start is tabulated as the number and percentage of subjects in each time category (i.e., month and year of LTT start date) for the full analysis set. See Section 7.1 for derived dates.

### **6.2.3     *Subject Disposition***

Subject disposition is based on the Study Exit Status case report form (CRF), unless noted otherwise. Note that the Study Exit Status CRF links non-completion due to AE to the AE CRF using numeric variables.

Refer to the Zavegeptan Core SAP for displaying reasons for not completing a milestone.

A by-subject listing of subject disposition is provided for the enrolled analysis set based on the Study Exit Status CRF, and includes the following: study completion status (yes, no, ongoing); reason for not completing the study, including specify text for “other” and AE preferred terms (PTs); LTT start date; LTT end date; study drug start date; study drug end date; last contact date; previous study treatment group(s); and previous study subject identifier. The listing also identifies subjects who terminated the study prematurely due to COVID-19 (see Section 9.1.4). See Section 7.1 for derived dates.

A by-subject listing of eligibility with inclusion and exclusion criteria is provided for all subjects in the enrolled analysis set, not just those who have non-missing criteria. This is based on the Inclusion/Exclusion Criteria CRF.

#### **6.2.3.1     *Subject Disposition from Enrollment to LTT Participation***

Subject disposition from enrollment to LTT participation is tabulated for the enrolled analysis set as the number and percentage of subjects in the following categories:

- LTT participated (identified as those with non-missing IWRS baseline visit date).
- Not LTT participated (identified as those with missing IWRS baseline visit date)
  - Did not enter the OP (identified as those with missing OP start date)
    - Reasons for early discontinuation (i.e., not completing the DBT Phase), including not reported. For subjects whose reason is screen failure due to inclusion/exclusion criteria, the reasons for screen failure from the Inclusion/Exclusion Criteria CRF are also included as subcategories.
    - Entered the OP (identified as those with non-missing OP start date)
      - Reasons for early discontinuation, including not reported. For subjects whose reason is screen failure due to inclusion/exclusion criteria, the reasons for screen failure from the Inclusion/Exclusion Criteria CRF are also included as subcategories.
  - Not LTT participated and terminated the study prematurely due to COVID-19 (see Section 9.1.4). This has the same subcategories as “Not LTT participated”.

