## **7 CONVENTIONS**

### **7.1 Derived Dates**

Derived dates for defining analysis periods are defined as follows:

- Study drug date/time: Complete finding date/time corresponding to “yes” response to question about taking study medication and number of sprays  $> 0$  in the eDiary evening report or medication reconciliation form.
- Study drug start date/time: Earliest study drug date/time.
- Study drug end date/time: Latest study drug date/time.
- Study drug last date/time: Study drug end date/time derived only for subjects with non-missing response to the question “Did the subject complete the study?” on the Study Exit Status CRF. Thus, in an interim analysis, all post-baseline data are included for a subject who is still on study. At the last database lock, the study drug last date is equal to the study drug end date.
- LTT start date/time: Earlier of (1) study drug start date/time, and (2) IWRS baseline visit date (i.e., Baseline/Day 1 visit date from the BHV3500\_202 IWRS Visit Report csv file).
- LTT end date/time: Later of (1) latest complete finding date/time in the eDiary on or after the LTT start date/time, and (2) latest complete visit date on or after the LTT start date through the Week 52/Early Termination visit date, and excluding the Follow-up Week 2 visit date, from the Visit Date CRFs.

- LTT last date/time: LTT end date/time derived only for subjects with non-missing response to the question “Did the subject complete the study?” on the Study Exit Status CRF. Thus, in an interim analysis, all LTT data are included for a subject who is still on study. At the last database lock, the LTT last date is equal to the LTT end date.
- OP start date/time: Earliest complete finding date/time in the eDiary before the LTT start date/time.
- OP end date/time: Latest complete finding date/time in the eDiary before the LTT start date/time.
- COVID-19 visit date: (1) Complete visit date, if it exists; (2) otherwise, complete date the visit was planned to occur for a missed visit (see Section 9.1.1).

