- Last contact date: (1) Earliest complete death date from the AE CRF, if it exists; (2) otherwise, the maximum complete date of the following: AE start or stop; COVID-19 visit only for in-person or remote visits; ECG; eDiary finding; informed consent; IWRS baseline visit; laboratory test collection; nasal inspection; non-study medication start or stop; physical exam; physical measurement; procedure; rating scale; questionnaire; vital sign; visit. If the last contact date is after the most recent raw database creation date, then it is set to the most recent raw database creation date.
- Death date: Last contact date derived only for subjects who died (see Section 6.4.1).

No imputations are performed on these derived dates. Complete dates are those with valid, non-missing day, month, and year.

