## 7.2 Analysis Periods

Analysis periods are defined as follows:

- OP: measurement date/time on or after the OP start date/time through the OP end date/time. This period is used to assess the number of migraine days per month during the OP.
- Pre-treatment: measurement date/time on or before the study drug start date/time. This period is used to derive baseline values, and to assess safety and outcomes research endpoints. Note that all measurements are pre-treatment for subjects in the enrolled analysis set with missing study drug start date.
- Pre-LTT: measurement date/time on or before the LTT start date/time. This period is used to derive analysis visit windows for slotting observations. Note that all measurements are pre-LTT for subjects in the enrolled analysis set with missing LTT start date.
- LTT: measurement date/time after the LTT start date/time through the LTT last date. This period is used to derive analysis visit windows for slotting observations, and to assess exposure and migraine days during LTT. Note that AEs with imputed start date equal to the

LTT start date are part of this period (refer to the Zavegeptan Core SAP for AE start date imputation).

- Follow-up: measurement date after the LTT last date. This period is used to slot observations.
- On-treatment safety: measurement date/time after the study drug start date/time through the study drug last date + 7 days. This period is used to assess safety endpoints on treatment.  
Note that AEs with imputed start date equal to the study drug start date are part of this period.
- Follow-up safety: measurement date after the study drug last date + 7 days. This period is used to assess safety endpoints during follow-up.

See Section 7.1 for derived dates for determining analysis periods. If measurement time is missing, not collected, or not applicable for a parameter, then the measurement date is compared to the derived date.

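### SAP 7.1 gives no observation-phase dates to subjects with neither a baseline visit date nor a dose, so the disposition table counts them all as never having entered that phase

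*SAP*

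**What the plan says.** SAP 6.2.3.1 tabulates disposition from enrollment to LTT participation for the enrolled analysis set. The group of interest is "Not LTT participated (identified as those with missing IWRS baseline visit date"). Within it there are two rows: "Did not enter the OP (identified as those with missing OP start date") and "Entered the OP (identified as those with non-missing OP start date"). Each row carries reasons for early discontinuation, with screen-failure criteria as subcategories. A further row, for non-participants who terminated because of COVID-19, repeats the same breakdown.

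The dates behind the split are defined in SAP 7.1:

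- "OP start date/time: Earliest complete finding date/time in the eDiary before the LTT start date/time". The OP end date is the latest such finding, with the same anchor.
- "LTT start date/time: Earlier of (1) study drug start date/time, and (2) IWRS baseline visit date".

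Elsewhere the SAP does provide for a missing LTT start date. For the pre-LTT analysis period, 7.2 says that "all measurements are pre-LTT for subjects in the enrolled analysis set with missing LTT start date", and 6.2.5.4 has explicit branches for pre-LTT medications. Neither the OP dates in 7.1 nor the OP analysis period in 7.2 has a corresponding rule.

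**The concern.** The two rows are meant to separate subjects lost at screening from those selected out during the 28-day observation phase. The variable that separates them depends on a date that people who fail before baseline do not have. A subject could complete four weeks of diary and still be reported as never having entered the phase.

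Such subjects will exist. The protocol starts evening reports after the screening visit (4.3.1). Several criteria can fail only after that point: the minimum number of treated attacks in the observation phase (inclusion 4e), headache days during it (inclusion 4f, exclusion 1b), diary compliance (exclusion 6g), and pre-baseline bilirubin and transaminases (exclusions 5f and 5h). Protocol 4.3.3 also makes unacceptable pre-baseline laboratory results a screen failure. The study report could therefore show a reason that refers to the observation phase under a row saying the subject never entered it. What is at stake is an accurate account of where untreated subjects left the study.

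**Working it through.** The documents state no figure for this split, so there is none to reproduce. The check is to follow the derivation and then bound the group.

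**Derivation**

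1. Not LTT participated means that the IWRS baseline visit date is missing (6.2.3.1).
2. LTT start = the earlier of study drug start and IWRS baseline visit date (7.1). If both are missing, LTT start is missing.
3. OP start = the earliest complete eDiary date earlier than LTT start (7.1). With LTT start missing, no diary date meets the condition, so OP start is missing.
4. A missing OP start means *Did not enter the OP* (6.2.3.1), however many diary days exist.

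I applied these rules to five invented subjects, first as written and then with a fallback that uses all complete eDiary dates when LTT start is missing. Days are counted from the first possible diary day.

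| Subject | IWRS baseline | First dose | Diary days | LTT start | As written | With fallback |
|---|---|---|---|---|---|---|
| A: fails at screening | none | none | none | missing | Did not enter | Did not enter |
| B: fails after full OP | none | none | 1–28 | missing | Did not enter | Entered (OP start day 1) |
| C: fails during OP | none | none | 1–10 | missing | Did not enter | Entered (OP start day 1) |
| D: dosed without IWRS date | none | day 30 | 1–59 | day 30 | Entered (OP start day 1) | unchanged |
| E: LTT participant | day 29 | day 33 | 1–379 | day 29 | LTT participated | unchanged |

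As written, A, B and C cannot be told apart, and only D reaches *Entered the OP*. D is the dosing deviation listed in 9.2, not a screen failure. The fallback moves B and C and nobody else.

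**Size**

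- Planned: about 800 screened and about 600 treated (Protocol synopsis; SAP 2.1).
- Not treated: 800 − 600 = 200, and 200/800 = 25% of those screened.
- Affected = 200 − (LTT participants never dosed). That second group has an IWRS baseline date and is tabulated separately in 6.2.3.2; its size is not given.
- Misclassified = affected − (those with no diary data, like subject A, who are classified correctly). That number is not given either.

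The number misclassified therefore lies between 0 and about 200, and the documents do not narrow it.

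**Other output that uses the OP dates**

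The 9.2 deviation for fewer than two treated attacks counts days in the OP analysis period, which 7.2 bounds by the OP dates. For these subjects the period is undefined. If that is programmed as zero days, they could be flagged whatever their diaries show. This would reach only the by-subject deviation listing, which covers the enrolled set. The deviation table uses the full analysis set (6.2.4.1), to which these subjects do not belong.

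**The case against.** The best reply is that the intent is plain. A row for non-participants who entered the OP makes sense only if some of them have an OP start date, and 7.2 already treats everything recorded for a subject without an LTT start date as pre-LTT. A programmer could carry that over to the diary dates. The intent is indeed clear, but the 7.2 note assigns measurements to the pre-LTT period. It does not define the OP start date that 6.2.3.1 tests, and nothing in the SAP extends it.

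It is tempting to add that 7.1 rules out any repair because "No imputations are performed on these derived dates". That sentence carries little weight. The text after it defines complete dates, so it appears to be about partial dates, and using an observed, complete diary date is not imputation.

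Three further points for the plan stand. The failure reasons are printed as subcategories in whichever row applies, and some of them name the observation phase themselves. SAP 6.2.3 also provides a by-subject eligibility listing for all enrolled subjects, so much of the split can be reconstructed. An almost empty *Entered the OP* row would probably be noticed in a dry run. Finally, the mock TLF document and the Zavegepant Core SAP are not available, so what would actually be programmed cannot be confirmed. SAP 6.2.3 itself cites the Core SAP only for how reasons are displayed.

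**Conclusion.** The point holds as a defect in a stated rule. For enrolled subjects with neither an IWRS baseline visit date nor a study drug start date, 7.1 yields no OP dates, and 6.2.3.1 then counts all of them as not having entered the OP. The row meant for observation-phase failures is left with, at most, subjects dosed without an IWRS date. The COVID-19 termination row has the same fault.

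The ceiling is about 200 of 800 planned subjects (25%), on the assumption that the planned numbers are met.

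The documents do not support three stronger readings:

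- *Every screen failure is misclassified.* Those who never made a diary entry are placed correctly.
- *About 200, or some stated share of them, are misclassified.* The 200 includes any LTT participants never dosed, and the documents give no proportion failing after the diary starts.
- *The safety results are distorted.* Treated subjects have a study drug start date and hence an LTT start date. Their OP dates, the migraine analysis set and the primary safety endpoints do not change.

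The effect is confined to the disposition split and other OP-based outputs for untreated subjects. It is worth correcting before the table is produced, but no conclusion about the drug depends on it.

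**What to change.** In SAP 7.1, keep the current OP start and end definitions for subjects who have an LTT start date. Add that, when the LTT start date is missing, the OP start (end) date/time is the earliest (latest) complete eDiary finding date/time on record.

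Sections 6.2.3.1, 7.2 and 9.2 then work without change. The cost is one sentence in the SAP and one extra branch in the derivation code. It uses data already collected and alters no date for any subject who has an LTT start date.

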#### **6.2.3.2     *Subject Disposition from LTT Participation to Treatment***

Subject disposition from LTT participation to treatment is tabulated for the LTT participated analysis set as the number and percentage of subjects in the following categories:

- Treated with study drug (identified as those with non-missing study drug start date)

- Not treated with study drug (identified as those with missing study drug start date)
  - Reasons for early discontinuation (i.e., not completing the DBT Phase), including not reported
- Not treated with study drug and terminated the study prematurely due to COVID-19 (see Section 9.1.4)
  - Reasons for premature termination, including not reported.

#### 6.2.3.3 *Subject Disposition from Treatment through Follow-up*

Subject disposition from treatment through follow-up is tabulated for the safety analysis set as the number and percentage of subjects in the following categories:

- Ongoing in the study (identified as those with missing response to the question “Did the subject complete the study (including the follow-up visit)?”). This category only exists before the final database lock. After the final database lock, subjects with missing response are categorized as “Did not complete the study”.
- Completed the study (identified as those with “yes” response to the question “Did the subject complete the study (including the follow-up visit)?”)
- Did not complete the study (identified as those with “no” response to the question “Did the subject complete the study (including the follow-up visit)?”)
  - Reasons for early discontinuation, including not reported
- Terminated the study prematurely due to COVID-19 (see Section 9.1.4)
  - Reasons for premature termination, including not reported.

#### 6.2.3.4 *Overall Premature Study Termination due to COVID-19*

Overall premature study termination due to COVID-19 is tabulated for the enrolled analysis set as the number and percentage of subjects in categories defined by reasons for premature termination, including not reported.

#### 6.2.3.5 *Treatment in Previous Studies*

Treatment in previous studies BHV3500-201 and BHV3500-301 is tabulated for the following analysis sets: enrolled; LTT participated; safety. The number and percentage of subjects who took study drug in each previous study (total; 201; 301) and as-treated treatment group (zavegepan, placebo) are presented for each analysis set together in a single table. Note that subjects may take study drug in multiple studies and be in both treatment groups.

## **6.2.4 Protocol Deviations**

### **6.2.4.1 Relevant Protocol Deviations**

Relevant protocol deviations are tabulated as the number and percentage of subjects with deviations by deviation type (eligibility, subject management), category, and subcategory in the order specified in Section 9.2 for the full analysis set. Results for all relevant protocol deviation categories and subcategories are displayed, even those with 0 counts, unless specified otherwise.

A by-subject listing of relevant protocol deviations is provided for the enrolled analysis set. This includes deviation type, category, and subcategory, which are used as additional sorting variables.

### **6.2.4.2 Significant Protocol Deviations**

A by-subject listing of significant protocol deviations is provided for the enrolled analysis set. This includes date of deviation, category, (e.g., Eligibility Criteria), subcategory (e.g., Violation of Exclusion Criteria), and description, which are used as additional sorting variables.

A Microsoft Excel file of protocol deviations is extracted from the clinical trial management system (CTMS) by Biohaven Clinical Operations. This file serves as the raw data source of protocol deviations, and classifies deviation severity as major, minor, or downgraded from protocol deviation. Significant protocol deviations are defined as those with major severity.

